5.11 Hospitalization and Other Clinical Events

Times to the following clinically relevant events are defined:

- Time to first hospitalization due to a serious adverse event (SAE),
- Time to first hospitalization due to an ALS-related SAE,
- Time to first use of assisted ventilation,
- Time to first placement of a feeding tube,
- Time to King's stage 4a or 4b, and
- Time to first instance of hospitalization for an SAE, feeding tube placement, tracheostomy, initiation of PAV, or death.

Time at risk for each event will be measured from each participant's Baseline Visit. Time to first hospitalization excludes hospitalizations for elective procedures. ALS-related SAEs are those indicated as related to ALS disease progression by the site investigator. Participants who are already using assisted ventilation or have a feeding tube at the time of the Baseline Visit will be excluded from analysis of those endpoints. Death or death equivalent will be considered an outcome for each of the events listed, forming a composite endpoint.

Time at risk for these events will be censored at the Week 24 Visit, if completed, the date of consent withdrawal, if withdrawn, or the last date at which the status of each endpoint is known prior to the end of the Week 24 Visit window for participants lost to follow-up. Time to King's stage 4a or 4b is interval censored between ALSFRS-R assessments.

5.12 Pharmacodynamic Biomarkers

Complement functional activity will be assessed by complement-mediated lysis using the sheep RBC hemolysis assay and will be quantified by the serum or CSF dilution resulting in 50% haemolytic complement (CH50) activity. C5 concentrations in plasma and CSF will be assessed by enzyme-linked immunosorbent assay (ELISA).

5.13 Clinical Safety Laboratory Tests

Clinical safety labs include hematology, blood chemistry panel, liver function tests, thyroid function, urinalysis, and pregnancy testing in women of childbearing potential as specified in Section 9.1.2 Clinical Safety Laboratory Tests of the Master Protocol:

- Hematology: hematocrit, hemoglobin, platelet count, red blood cell (RBC) count, mean corpuscular volume, mean corpuscular hemoglobin, mean corpuscular hemoglobin concentration, RBC distribution width (RDW), RBC morphology, white blood cell (WBC) count, and counts and percentages of basophils, eosinophils, lymphocytes, monocytes, and neutrophils;
- Blood chemistry panel: bicarbonate, chloride, potassium, sodium, calcium, magnesium, phosphate, blood urea nitrogen, creatinine, estimated glomerular filtration rate (eGFR) calculated using the Modification of Diet in Renal Disease (MDRD) four-variable equation, creatinine clearance calculated using the Cockcroft-Gault equation, and glucose;
- Liver function tests: alanine aminotransferase (ALT [SGPT]), aspartate aminotransferase (AST [SGOT]), alkaline phosphatase (ALP), albumin, total protein, total bilirubin (TBL);
- Thyroid function tests: thyroid-stimulating hormone (TSH);
- Urinalysis: clarity, color, specific gravity, pH, microalbumin, protein, glucose, ketones, bilirubin, urobilinogen, nitrite, leukocyte esterase, and blood; and
- Pregnancy: qualitative and quantitative serum human chorionic gonadotropin (hCG).

Clinical safety labs will also include derived measures of potential drug-induced liver injury (DILI), including those that potentially meet the Hy's law criteria, as distinct safety lab outcomes.

Three potential DILI criteria will be defined:

- ALT or AST $>3x$ ULN with TBL $>1.5x$ ULN
- AST or ALT $>3x$ ULN with TBL $>2x$ ULN
- AST or ALT $>3x$ ULN with TBL $>2x$ ULN and ALP $<2x$ ULN (potential Hy's Law cases)

where ULN is upper level of normal and all levels are measured on the same day.

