2.9 RGA Schedule of Activities (SoA)

Activity	MP Scrn ¹	RGA Scrn ²	Base-line	Week 2	Week 4	Week 8 ³	Week 12	Week 16 ³	Week 20	Week 24 ³	Final Call ⁴
	Cln	Cln	Cln	Phn	Cln ⁵	Cln ⁵	Phn	Cln ⁵	Phn	Cln	Phn
	-42d to -1d	-41d to 0d	Day 0	Day 14±3	Day 28±7	Day 56±7	Day 84±3	Day 112±7	Day 140±3	Day 168±7	40d ±3
Written Informed Consent ⁶	X	X ⁷									
Inclusion/Exclusion Review ⁸	X	X									
ALS & Medical History	X										
Demographics	X										
Physical Examination	X										
Neurological Exam	X										
Vital Signs ⁹	X		X		X	X		X		X	
Slow Vital Capacity	X ¹⁰		X			C		C		X	
Home Spirometry	X ¹⁰		X		X			X		X	
Muscle Strength Assessment			X			C		C		X	
ALSFRS-R	X		X		X	X	X	X	X	X	
ALSAQ-40			X							X	
CNS-BFS			X			X		X		X	
12-Lead ECG	X									X	
Clinical Safety Labs ¹¹	X		X		X	X		X		X	
Anti-drug Antibody Sampling			X			C		C		X	
Zilucoplan PK Analysis ¹²			X			C		C		X	
Zilucoplan PD Analysis ¹²			X			C		C		X	
Zilucoplan Biomarker Samples ¹²			X			C		C		X	
Biomarker Blood Collection ¹²			X			C		C		X	
Biomarker Urine Collection ¹²			X			C		C		X	
DNA Collection ¹³ (optional)			X								
CSF Collection (optional)			X					C ¹⁴			
Concomitant Medication Review	X	X	X	X	X	X	X	X	X	X	
Adverse Event Review ¹⁵	X	X	X	X	X	X	X	X	X	X	X
Suicidality C-SSRS			X		X	X		X		X	

Activity	MP Scrn ¹	RGA Scrn ²	Base-line	Week 2	Week 4	Week 8 ³	Week 12	Week 16 ³	Week 20	Week 24 ³	Week 24 ³	Final Call ⁴
	Cln	Cln	Cln	Phn	Cln ⁵	Cln ⁵	Phn	Cln ⁵	Phn	Cln	Phn	
	-42d to -1d	-41d to 0d	Day 0	Day 14±3	Day 28±7	Day 56±7	Day 84±3	Day 112±7	Day 140±3	Day 168±7	Day 40d ±3	ALD
Install Smartphone Apps ¹⁶			X									
Smartphone Voice Recording ¹⁷			X		X	X			X		X	
Uninstall Smartphone App											X	
Regimen Assignment	X											
Randomization within RGA			X									
Administer/Dispense Study Drug			X ¹⁸		X	C		C				
Drug Accountability/Compliance				X ¹⁹	X	X	X ¹⁹	X	X ¹⁹	X		
Exit Questionnaire											X	
N. meningitidis Vaccination		X ²⁰			X	X					X	
Vital Status											X ²¹	

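### The three liver-injury flags require same-day values, so a bilirubin rise seen only after ALT/AST has fallen to 3x ULN or below is counted by none of them

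*SAP*

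**What the plan says.** SAP 5.13 adds derived liver-injury measures to the clinical safety labs and treats them "as distinct safety lab outcomes". It states "Three potential DILI criteria will be defined":

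1. ALT or AST above 3x ULN with total bilirubin (TBL) above 1.5x ULN.
2. ALT or AST above 3x ULN with TBL above 2x ULN.
3. As criterion 2, with ALP below 2x ULN (potential Hy's law cases).

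One closing clause governs all three: "all levels are measured on the same day". The supplied documents give no time window, no version based on peak values and no exception.

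The schedule in SAP 2.9 places post-baseline clinical safety labs at Weeks 4, 8, 16 and 24 (days 28, 56, 112 and 168, each ±7 days).

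Two other outputs touch the liver. SAP 6.6.2 puts each participant's worst post-baseline toxicity grade, within 40 days of last dose, into shift tables. SAP Appendix 1 lists drug-related hepatic disorders among the adverse events of interest, found by a narrow search on reported terms.

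**The concern.** The flags screen for rare, serious events, and in such a screen a missed case costs more than an extra case to review. Bilirubin can rise later than the transaminases. If ALT/AST has come down to 3x ULN or below by the draw at which bilirubin is first over its limit, no single day satisfies any criterion, although both limits were exceeded during treatment.

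The plan allows some tolerance in another multi-component safety screen: the anaphylaxis algorithm in Appendix 1 accepts components on the same day or on two consecutive days. It also already uses a worst-value-over-follow-up summary in 6.6.2. The liver flags use neither device, although the scheduled draws that feed them are weeks apart.

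At stake is whether the safety report shows no potential case, or one or more that need medical review.

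**Working it through.** The plan attaches no figure to these flags, so there is nothing to reproduce. The check applies the definitions as written.

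**Inputs from the documents**
- Criteria and same-day clause: SAP 5.13.
- Draw days 28, 56, 112 and 168: SAP 2.9.
- 40-day limit after last dose: SAP 6.6.2.
- About 120 participants planned on active treatment: protocol RSA summary.

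**Spacing of scheduled draws**
- Week 4 to Week 8: 56 − 28 = 28 days nominally; with ±7-day windows, 14 to 42.
- Week 8 to Week 16: 112 − 56 = 56 days; with windows, 42 to 70.
- Week 16 to Week 24: 168 − 112 = 56 days; with windows, 42 to 70.

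**Rules compared**
- Same-day: some day has ALT/AST > 3 and TBL > 1.5 (criterion 1) or > 2 (criterion 2), plus ALP < 2 that day (criterion 3).
- Window of w days: a day with ALT/AST > 3, followed 0 to w days later by TBL over its limit; for criterion 3, ALP < 2 on the ALT/AST day.
- Peak pairing: maximum ALT/AST > 3 and maximum TBL over its limit, in any order; for criterion 3, ALP < 2 on the day of peak ALT/AST.

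**Four hypothetical courses** (all values are assumptions, in multiples of ULN; ALP is 1.2 at the first draw shown, and 1.3 at the second in A to C). Each result is the same for all three criteria.

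| Course | First draw | Next draw | Same-day | 14-day window | 30-day window | 60-day window | Peak pairing |
|---|---|---|---|---|---|---|---|
| A | day 28: ALT 8, TBL 1.0 | day 56: ALT 4, TBL 2.5 | counted | counted | counted | counted | counted |
| B | day 28: ALT 8, TBL 1.0 | day 56: ALT 2.5, TBL 2.5 | missed | missed | counted | counted | counted |
| C | day 56: ALT 8, TBL 1.0 | day 112: ALT 2.5, TBL 2.5 | missed | missed | missed | counted | counted |
| D | day 28: ALT 8, TBL 2.5 | day 56: ALT 2, TBL 1 | counted | counted | counted | counted | counted |

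In B and C the second draw has TBL 2.5 > 2 but ALT 2.5 ≤ 3, and the first has ALT 8 > 3 but TBL 1.0 ≤ 1.5, so no day satisfies any criterion. Peak pairing gives ALT 8 > 3, TBL 2.5 > 2 and ALP 1.2 < 2, so all three are met. In A the bilirubin rise also follows the transaminase peak, yet the case is counted because ALT is still 4x ULN that day.

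A fixed window has to allow for the draw spacing: 30 days recovers B but not C. Peak pairing needs no window, but it requires each elevation to be seen at some draw.

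**Other outputs.** In course B, the toxicity shift tables would show the worst ALT and the worst bilirubin as separate entries, not as a pair. The adverse event search finds the participant only if a hepatic term was reported.

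**What one case would mean.** For 0 of 120, the exact two-sided 95% upper bound is 1 − 0.025^(1/120) = 3.0%. For 1 of 120, it solves (1 − p)^120 + 120p(1 − p)^119 = 0.025, giving p = 4.6%. This shows the effect of one case on the report; it does not estimate how many would be missed.

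**The case against.** A reader might infer that any case in which bilirubin rises after the transaminase peak is lost. The documents do not support that. The clause requires ALT/AST above 3x ULN on the day bilirubin is over its limit; it does not require bilirubin to coincide with the peak. Course A is counted. Nor must every limit be exceeded for the Hy's law flag: there ALP is a ceiling to stay under.

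A reader might also picture unscheduled repeat liver tests that catch the two elevations days apart. The supplied documents describe none. As-needed repeats appear only for pregnancy testing (SAP 2.9), and unscheduled visits only for antibody status (SAP Appendix 2). Any such rule would be in the Master Protocol, which was not supplied. The point rests on the scheduled gaps alone.

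The rest of the case against is as follows.

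- The rule is explicit, prespecified and reproducible, and it contradicts nothing else. This stands: it is a choice, not an error.
- Pairing peaks over 24 weeks plus 40 days can join unrelated events months apart. This also stands, and is why the supplementary flag needs a dated listing and should not replace the same-day flags.
- The participant is not invisible, because single-analyte tables and hepatic adverse events remain. True, but neither pairs the two analytes.
- SAP 6.6.2 otherwise defers safety-lab analyses to the Master SAP, which may already contain a peak-value display. This cannot be checked from the supplied documents.

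**Conclusion.** The point holds in a limited form, as a cheap improvement. No flag counts a participant whose bilirubin first exceeds its limit only after ALT/AST has fallen to 3x ULN or below, or whose two elevations are each seen but never in one draw. Draws 28 to 56 days apart leave room for this.

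The frequency is unknown, and the documents give no liver data from which to estimate it. Saying that cases will be missed, or that one missed case would be the whole signal, goes beyond what they support.

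The conclusion assumes that the same-day clause is applied literally and that the Master SAP adds no non-concurrent version. It concerns only how cases are counted in the report; it bears on no efficacy analysis and no clinical rule.

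**What to change.** Keep the three same-day flags unchanged. In SAP 5.13, add a supplementary flag for each criterion:

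- Pair the participant's peak post-baseline ALT/AST with peak post-baseline TBL, both within 40 days of last dose (the period already used in 6.6.2), with the same limits.
- For the Hy's law version, take ALP on the day of peak ALT/AST. This timing must be stated: with peak ALP, a later ALP rise could remove a participant whom the same-day flag counts.
- List dates and values of ALT, AST, TBL and ALP for every participant who meets either kind of flag, so that temporally unrelated pairs can be identified on medical review.

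Report the two sets of flags side by side. Because the same-day flags stay, no case now counted is lost.

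The cost is one derivation per criterion and one listing, from data already collected. The downside is a few extra cases that prove unrelated. If the Master SAP already provides such a display, a cross-reference in 5.13 is enough.

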5.14 Immunogenicity

Blood samples will be screened for ADA and anti-PEG-ADA by ELISA. Samples screening positive will be further tested for immunodepletion. The ADA and anti-PEG-ADA status of each sample will be classified as follows:

- Negative: sample values that are either "negative screen" or "positive screen" and "negative immunodepletion",
- Positive: sample values that are "positive screen" and "positive immunodepletion", or
- Missing: samples that could not be tested due to inadequate sample volume, mishandling, or errors in sample collection, processing, or storage.

6. Statistical Methodology

6.1 Analysis Sets

The ITT analysis set is henceforth referred to as the Full Analysis Set (FAS) and defined as follows:

- Full Analysis Set (FAS): Participants who were randomized within RGA plus placebo participants from specified regimens, classified according to their randomized treatment assignment. Observations made after premature permanent discontinuation of study drug are included in this sample, should such participants remain on study. Observations completed after regimen data lock are excluded. Participants determined to not meet ALS diagnostic criteria are excluded.

The definition of the STF analysis set is revised as follows:

- Safety Full (STF) Set: Participants who initiated treatment within RGA plus placebo participants from specified regimens who are not known to be ineligible for RGA and who initiated treatment in their respective regimen, classified according to the treatment they actually received. Observations made after premature permanent discontinuation of study drug are included in this sample, should such participants remain on study. Observations completed after regimen data lock are excluded.

An analysis set restricting shared placebo participants to those regimens in which study drug is administered by the same route as RGA is defined as follows:

- Efficacy Common Mode of Administration (ECM) Set: The subset of participants in the FAS analysis set who are in regimens in which study drug is administered by the same route as RGA.

The definitions of the ECC, ERO, STN, and SRO analysis sets are the same as described in the M-SAP with reference to the ITT analysis set now referencing the FAS analysis set. The following analysis set is specific to RGA:

- Efficacy Per-protocol (EPP) Set: The subset of participants in the FAS analysis set who initiated study treatment and who were not involved in protocol deviations that affected the scientific integrity of the trial as documented prior to data lock, classified according to the treatment they actually received. Inclusion or exclusion from the EPP analysis set of any participant for whom treatment assignment was unblinded prior to data lock will be governed by the prespecified criteria above. If a participant's data is truncated for inclusion in the EPP analysis set due to non-adherence to protocol-specified dosing, clinical events observed up to 40 days after the censoring event will be included in the EPP analysis set. For all other events leading to truncation of a participant's data, no events beyond that date will be included. Data from placebo participants shared from other regimens will not be truncated due to non-adherence to protocol-specified dosing.

Applicable analysis sets (FAS, EPP, and STF) will include shared placebo participants from regimens B, C, and D. Data from shared placebo participants will include visits and events that occurred on or before the date of the final placebo-controlled period follow-up of an RGA participant. As only concurrently enrolling regimens are contributing to efficacy analyses, the FAS and ECC analysis sets are synonymous and only the FAS analysis set will be referenced. As

RGA is the only regimen administering study drug by subcutaneous injection among those contributing to safety analyses, the ECM and ERO analysis sets and the STN and SRO analysis sets are synonymous and only the ERO and SRO analysis sets will be referenced.

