3.0 (continued)	22 Jul 2022 (continued)	
Revision of Section 5.9 Survival to specify that time at risk begins at each participant's Baseline Visit and to specify that the date of PAV initiation, where applicable, will be imputed as the fifteenth day of a month if not specified more precisely.
 
Revision of Section 6.1 Analysis Sets to add the Efficacy Common Mode of Administration (ECM) analysis set, to remove the restriction on protocol deviations that could be considered for exclusion from the Efficacy Per-protocol (EPP) analysis set must be classified as major protocol deviations, to specify the time point at which data is excluded from the EPP analysis set in the case of time-dependent exclusions, and to specify that data from placebo participants from other regimens would not be excluded from the EPP analysis set due to non-adherence to protocol-specified dosing.
 
Revision of Section 6.2 Baseline Characterization to include ALSAQ-40 domain scores and SI.
 
Revision of Section 6.5.2 Repeated-measures Model to add a fixed term for treatment group (removing the shared-baseline assumption at the recommendation of the FDA) and to specify a separate supportive analysis that includes fixed terms for centered baseline serum NfL level, and centered baseline serum NfL level \times visit interaction.
 
Revision of Section 6.5.3 Random-slopes Model to add a fixed term for treatment group (removing the shared-baseline assumption) and to specify a separate supportive analysis that includes fixed terms for centered baseline serum NfL level, and centered baseline serum NfL level \times study month interaction.
 
Revision of Section 6.5.4 Survival and Time to Clinical Events to clarify that survival analyses that include follow-up beyond the placebo-controlled period will be analyzed in the ERO analysis set, to include baseline age as an additional covariate in adjusted models given strong prognostic value, and to specify an additional adjusted analysis that includes baseline serum NfL level as a covariate.
 
Revision of Section 6.5.5 CAFS to clarify that the primary CAFS analysis is specified in the ALS Master Protocol Recommended Statistical Analysis, Design and Simulation Report and to add two additional sets of CAFS analyses that adjust rank scores in linear models, one set that adjusts for time from ALS symptom onset, delta-FRS, baseline use of riluzole, and one set that adjusts

Version	Date	Description of Changes

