6.3 Primary Efficacy Analysis and Supportive Analyses

The primary analysis for RGA is a Bayesian shared-parameter, repeated-measures model of ALSFRS-R that accounts for loss of follow-up due to mortality. Details of the model, including documentation of operating characteristics under a range of scenarios, are provided in the "ALS Master Protocol Recommended Statistical Analysis, Design and Simulation Report" (Appendix 1 to the Master Protocol). The Bayesian shared-parameter, repeated-measures model will be applied to the FAS analysis set as the primary analysis, to the ERO analysis set as a sensitivity analysis, and to the EPP analysis set as a supportive analysis.

The estimand of the primary analysis is the relative rate of disease progression (the "disease rate ratio" or DRR) of active treatment relative to placebo in the FAS population under an assumption that active treatment slows mean time to death or death equivalent by the same proportion as treatment slows the mean rate of functional progression as measured by change in ALSFRS-R total score over time. The estimand is defined by the following attributes:

- Treatment: zilucopan administered subcutaneously once daily at a dosage of approximately 0.3 mg/kg vs. placebo.
- Population: FAS population as defined in Section 6.1.
- Variables: time to death or death equivalent and rate of change in ALSFRS-R total score from baseline to the Week 24 Visit.
- Intercurrent event 1: treatment discontinuation due to death: no ALSFRS-R data from participants who reach the death or death equivalent endpoint are included in the analysis, handled via mortality component in model, composite variable strategy approach.
- Intercurrent event 2: treatment discontinuation not due to death: handled via treatment policy approach, all data will be used including data collected during the placebo-controlled period after treatment discontinuation regardless of concomitant medication, for those participants who have not been censored due to mortality. Missing data post-treatment will not be imputed, handled via missing at random assumption.
- Population-level summary: mean ratio of hazard or progression rate of active treatment relative to placebo.

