6.5 Secondary Efficacy Analyses

6.5.1 Hierarchical Testing

Primary inference for secondary efficacy endpoints will be based on analysis of the FAS analysis set using a repeated-measures linear mixed model for functional endpoints (see Section 6.5.2 below) and by Kaplan-Meier product-limit estimates and log-rank test for the primary survival endpoint (see Section 6.5.4 below). The sequence for testing secondary efficacy endpoints is the following:

1. HHD upper extremity percentage,
2. SVC,
3. HHD lower extremity percentage, and
4. Survival.

If the primary analysis indicates a significant slowing in disease progression from the Bayesian shared-parameter, repeated-measures model of ALSFRS-R and mortality, then each secondary efficacy endpoint in succession would be declared significant in the specified sequence using a comparison-wise criterion of two-tailed $p < 0.05$. After the first failure to declare significance, no endpoints lower in the hierarchy can be significant. This sequential closed-testing procedure controls the overall type 1 error rate at 5%. Nominal comparison-wise p-values for secondary efficacy endpoints will also be reported.

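### The supportive per-protocol (EPP) set truncates zilucoplan-regimen participants for dosing non-adherence but exempts shared placebo, so it can be biased with no drug effect; an RGA-only EPP avoids the unequal rule

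*SAP*

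**What the plan says.** SAP 6.1 defines EPP as a subset of the Full Analysis Set (FAS) and provides for truncating data for non-adherence to dosing. After such truncation, "clinical events observed up to 40 days after the censoring event will be included in the EPP analysis set". The exemption follows: "Data from placebo participants shared from other regimens will not be truncated due to non-adherence to protocol-specified dosing". The same section brings in the external controls: "Applicable analysis sets (FAS, EPP, and STF) will include shared placebo participants from regimens B, C, and D".

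The exemption was deliberate. The SAP revision history for version 3.0 records that "data from placebo participants from other regimens would not be excluded from the EPP analysis set due to non-adherence to protocol-specified dosing", without a reason. SAP 6.1 sets no cut-off for non-adherence. Protocol 5.7 makes 10 or more consecutive missed doses a major deviation, which reaches EPP only indirectly, through its deviation criterion.

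On the role of EPP, SAP 6.3 applies the primary Bayesian model to FAS, to ERO (RGA participants only, not truncated) as a sensitivity analysis, and "to the EPP analysis set as a supportive analysis". SAP 6.5.4 also uses EPP as one of several sets for survival and clinical events. For the hierarchy, SAP 6.5.1 says "Primary inference for secondary efficacy endpoints will be based on analysis of the FAS analysis set".

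**The concern.** Whether a participant is truncated depends on behaviour after randomisation. Active and RGA placebo participants are both subject to the rule. Shared placebo participants are followed in full, whatever their dosing. The two sides of the comparison are therefore handled differently, and a difference can appear with no drug effect.

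- If those who stop are faster progressors in a way their scores do not yet show, EPP leans towards zilucoplan.
- If slower progressors stop, or decline slows after stopping, it leans against zilucoplan.
- If stopping is random or depends only on recorded scores, a likelihood-based slope model allows for it.

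EPP survival and event comparisons lack that last protection unless they adjust for those scores. The covariates that SAP 6.5.4 adds, age and serum NfL, are baseline ones.

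At stake is interpretation. An EPP–FAS difference could not be read as an effect of adherence. It would also mix in EPP exclusions and classification by treatment actually received.

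**Working it through.** **Inputs from the documents.** About 160 participants at 3:1 (Protocol, Number of Planned Participants and Treatment Groups); 24 weeks; 40-day event window (SAP 6.1); missing-at-random assumption (SAP 6.3). **Assumed:** number of shared placebo S, stopping rate, stopping mechanism and progression parameters.

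**1. Planned arms.** 160 × 3/4 = 120 active and 160 × 1/4 = 40 placebo, as the protocol states. The documents give no bias or error figure for EPP.

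**2. Share of controls under the rule.** 40/(40+S): 40/80 = 50%, 40/120 = 33%, 40/160 = 25% for S = 40, 80, 120. In the active arm it is 100%.

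**3. First null simulation (true DRR 1.00; below 1 favours zilucoplan).** 150,000 subjects per scenario. ALSFRS-R at weeks 0, 4, 8, 12, 16, 20 and 24; slope −1.1/month (SD 0.8), intercept SD 6, residual SD 1.5; 8% death or permanent ventilation by week 24, with hazard tied to slope. Scores are cut at the stop and deaths counted to stop + 40 days. DRR is the precision-weighted combination of the log slope ratio and log death-rate ratio. Results for S = 120, all stoppers still assessed:

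| Who stops | DRR at 10 / 20 / 30% stopping | Death-rate ratio |
|---|---|---|
| Random | 1.00 at each rate | – |
| Recorded decline, coefficient 1 per SD | 1.000 / 1.000 / 1.001 | 0.988 / 0.978 / 0.969 |
| Recorded decline, coefficient 2 per SD | 1.000 / 0.999 / 0.999 | 0.980 / 0.962 / 0.947 |
| Latent faster progressors | 0.977 / 0.958 / 0.940 | – |
| Latent slower progressors | 1.025 / 1.046 / 1.061 | – |
| Half-speed decline after stopping | 1.019 / 1.040 / 1.061 | – |

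With S = 40 or 120 and 50% or 100% of stoppers still assessed, the ranges are 0.940–0.992 (faster stop), 1.009–1.062 (slower stop), 1.006–1.061 (half speed) and 0.999–1.006 (recorded decline). The largest shift is about 0.6 of the standard error of log DRR. SAP 6.3 says "no ALSFRS-R data from participants who reach the death or death equivalent endpoint are included in the analysis"; dropping those scores changes DRR by at most 0.007.

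At trial size (5,000 runs, S = 120, 20% stopping) the pooled slope shifts are +0.045, −0.049 and −0.041 points/month in the three biased cases, with two-sided rejection of 0.058–0.061 at nominal 5%.

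**4. Second null simulation, other assumptions.** 2,000–3,000 trials per scenario, S = 120, slope −1.0/month, residual SD 2. Positive bias favours zilucoplan.

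| Stopping | Slope bias, points/month | Two-sided error |
|---|---|---|
| Recorded scores | −0.001 | 5.1–5.2% |
| Latent slope, OR 2 per SD, 20% | +0.053 | 6.9% |
| Latent slope, OR 3 per SD, 30% | +0.124 | 18.9% |
| Unrecorded acceleration 1.0/month, 20% | +0.096 | 13.1% |
| Unrecorded acceleration 1.0/month, 30% | +0.144 | 22.4% |
| Slower progressors, OR 1/2 per SD, 20% | −0.055 | 8.2% |

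Where faster or accelerating progressors stop, apparent slope ratios run from 0.86 to 0.98. Apparent event hazard ratios are 0.90–0.99 when stopping is linked to prognosis, despite the 40-day window. FAS and ERO show at most 0.006 bias throughout.

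**5. Remedies.** RGA-only EPP, both RGA arms stopping alike: DRR 1.00 in every case of the first simulation; bias −0.004 to +0.006 in the second. One truncation rule for all controls (S = 120, 20% stopping) gives:

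- 1.000 if stopping is alike across regimens;
- 0.958 if only RGA stopping is severity-linked (0.957 under the current rule);
- 1.043 if only shared-placebo stopping is severity-linked (1.000 under the current rule).

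**6. Cost of RGA-only.** Interval ratio = √[(1/120 + 1/40) / (1/120 + 1/(40+S))]. The numerator is 0.03333. The denominators for S = 40, 80, 120 are 0.02083, 0.01667 and 0.01458, giving 1.265, 1.414 and 1.512.

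**The case against.** The strongest reply is that no planned decision depends on EPP: the primary analysis and the hierarchy use FAS, and ERO is an untruncated RGA-only check. That stands, and it sets the priority of this point. ERO does not answer the per-protocol question, however, because it is not truncated for non-adherence.

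The sizes are fragile. The first simulation's largest shift is about 0.6 of a standard error; the second reaches 0.144 against 0.121, more than one. Regimen random effects, which the SAP mixed models include, remove a little over a third in the first simulation and about a third in the second (for example +0.144 to +0.092). A baseline covariate such as pre-baseline slope, correlated 0.3, 0.5 or 0.7 with the true slope (assumed), would remove roughly 6%, 18% or 38%. So the bias shrinks without vanishing. Whether the Bayesian model has such terms is in a report not supplied.

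The Master SAP is also not supplied. SAP 6.5.4 takes its adjusted survival models from it, so the crude death-rate ratios may overstate the problem there, and SAP 6.5.9 defers sensitivity analyses to it. But SAP 6.1 presents EPP as specific to this regimen, and SAP section 1 gives the regimen SAP precedence over the Master SAP.

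The exemption can be defended: "RGA is the only regimen administering study drug by subcutaneous injection among those contributing to safety analyses", and extending one rule to shared placebo can itself create bias (1.043 above). That is a good reason to prefer RGA-only to uniform truncation.

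Finally, RGA-only is not a full cure. If the drug raises stopping (30% against 10%) without changing progression, it is still biased by +0.108/month, against +0.144 as written: 0.108/0.144 = 75% remains.

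**Conclusion.** The point holds, as a low-stakes improvement. Under no drug effect, EPP as written is biased when stopping reflects prognosis beyond the recorded scores, in a direction set by who stops. There is no material slope bias otherwise. Illustrative DRRs are 0.940 to 1.062, with slope ratios down to 0.86 under harsher assumptions. Mechanism and direction are firm. The sizes rest on assumed stopping rates, shared-placebo numbers and progression parameters, and on random-slopes approximations to the Bayesian model. No supplied section defines a per-protocol analysis that applies one dosing rule to both arms.

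**What to change.** Add to SAP 6.1 and 6.3:

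> The EPP analyses will also be run within RGA participants only (EPP within ERO), where active and placebo follow the same truncation rule. Per-protocol interpretation will rest on this version.

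Report the number truncated in active, RGA placebo and shared placebo. SAP 6.7.1 lists EPP exclusions and 6.7.6 summarises deviations by type and treatment group. Neither counts truncations or splits RGA from shared placebo, although deviations could be separated by comparing FAS with ERO.

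If a pooled EPP is kept, one option is a single non-adherence criterion, fixed before data lock and judged against each participant's own regimen, applied to shared placebo too. The SAP should then say that this removes the bias only if stopping behaves alike across regimens. It should also say that the RGA-only version removes the difference in rules, not per-protocol selection that arises when active and placebo participants stop for different reasons.

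The cost is two SAP sentences and one extra run of planned models on data already held. The wider interval, 1.26, 1.41 or 1.51 times the pooled one for 40, 80 or 120 shared placebo (assumed), affects only a supportive analysis.
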